The study participants are adults receiving treatment for COPD and their family caregivers. The patient participants must be older than 40 years, with no significant cognitive dysfunction, severe mental illness, or active substance abuse. Family caregivers must be 18 years or older and chosen by the patient participant to get enrolled with them into the study. The reason for these requirements is the nature of the proposed intervention (group-based with active engagement and participation).

[figure not shown]
We will conduct this study at Johns Hopkins Bayview Medical Center (JHBMC) and Howard County General Hospital (HCGH), and their affiliated pulmonary and primary care clinics (some of these clinics are part of Johns Hopkins Community Physicians). JHBMC is an academic center in Baltimore, Maryland that serves an urban, inner-city population with a large percentage of low-income and ethnic minority patients, as well as patients from the Baltimore-

Washington DC region. JHBMC has a 550-bed hospital, a nationally recognized pulmonary center, pulmonary specialty clinics, a pulmonary rehabilitation center, and multiple primary care clinics. HCGH is a community hospital in Columbia, Maryland that serves a suburban population with a large percentage of middle class patients, as well as patients from the Baltimore-Washington DC region. HCGH is a 300 bed community hospital, and includes pulmonary specialty clinics, a large pulmonary rehabilitation center (about 2000 people complete the acute rehabilitation program), and multiple primary care clinics. Both hospitals and their affiliated clinics are part of the Johns Hopkins Health System.

Study structure

We will conduct a randomized controlled trial (RCT) to implement and test study interventions at two study sites, recruiting COPD patient participants from an urban academic hospital (Johns Hopkins Bayview Medical Center) and its affiliated hospital based clinics and a suburban hospital (Howard County General Hospital) and its affiliated clinics. Participants will be recruited from both hospital and ambulatory service settings.

Below is a schematic depicting Phase 2 trial design:

* Randomize within site and service setting

In the HCP Arm, we will employ a healthcare professional delivered, clinic-based approach for engaging patients and families. It involves delivery of self-management education and support on an individual basis to individual patients (and their family caregivers, if applicable).

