The study will compare the impact of these strategies on the outcomes of health-related quality of life, mortality, and use of Emergency Department (ED) and other hospital services, as well as intermediate measures such as patient activation, self- efficacy, and self-care behavior, as described in the BREATHE2 Study Conceptual Model shown in Figure 1 below. At the same time, the study will compare the impact of these strategies on caregiver self-efficacy, stress, and coping skills. We will also assess both patient and caregiver experience and satisfaction within the HCP PLUS Peer Support Group.

[figure not shown]

Figure 1. BREATHE2 Study Conceptual Model

Study Design (PCORI Standard IR-1)

Phase 1 of this study involved intervention development followed by peer mentor recruitment and training. Phase 2 of this study, which is addressed by this SAP, involves rigorous testing of the study intervention in a randomized controlled trial (RCT) at two study sites: (1) Johns Hopkins Bayview Medical Center (JHBMC) and affiliated pulmonary and primary care clinics and (2) Howard County General Hospital (HCGH) and affiliated pulmonary and primary care clinics. (some of these clinics are part of Johns Hopkins Community Physicians). Thus within each study site, patients were recruited from two clinical settings: (1) inpatient recruitment within the hospital and (2) outpatient recruitment from the affiliated clinics.

We consented and enrolled 290 persons who met the initial eligibility criteria of receiving a physician diagnosis of COPD and treatment for it. Patient participants were randomized to one of the two study groups in this trial (HCP or HCP PLUS Peer Support) and their respective Caregiver Participant, if they have one enrolled, participated with them in that study group. Then patients were randomized 1:1 to the HCP or the HCP PLUS Peer Support.

Our primary study outcome is the change in quality of life (QOL) over the 6 months post discharge. Other patient measures include patient activation self-efficacy, self-care behavior,

health status, used of Emergency Department (ED) and other hospital services, and survival. Caregiver measures include caregiver self-efficacy, stress, and coping skills.

Intervention Description

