was calculated and was used to replace the value of the missing item responses before calculation of the scale/domain score. This approach weights the scale/domain score towards the respondent's mean response and is balanced by requiring a large majority of item responses to be available. If more than 25% of the item responses were missing, the scale/domain score was considered missing.

Statistical Analysis (PCORI Standard IR-1, RC-4)

Statistical summaries and distributions of patient characteristics will be reviewed by study site (JHBMC and HCGH) and by recruitment setting (inpatient and outpatient). Statistical summaries and distributions of patient and clinical characteristics will also be reviewed across study groups. Randomization of the patients to the study groups expects that on average the groups were balanced on characteristics that might affect the study results, such as socio-demographic and health status. Thus, no statistical tests to compare the groups on patient characteristics will be performed.¹¹

Exploratory analyses will be performed cross-sectionally at baseline, 3, 6, and 9 months post-discharge for each of the outcomes across the two study groups. This will provide an assessment of the outcomes' distributions, missingness patterns and the need for additional data review and quality assurance.

The main analysis approach for assessing the change in the primary outcome measure from baseline, as well as changes in secondary outcome measures from baseline, will consist of performing analyses of the treatment effect between the two study groups under intention to treat (ITT) adjusted for baseline measure, site, and recruitment setting.

Repeated outcomes in this study will be evaluated using generalized linear mixed random-effects (RE) models. The generalized linear mixed RE model reflects the study's interest in comparisons of change at the individual level, where the changes may be subject-specific and reflective of potentially unmeasured variables. This model also fits well with the approaches related to

missing data and heterogeneity of treatment effects discussed below. In particular, this approach will help us handle the missing 9-month data for participants who enrolled later in the study.

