The primary repeated outcome (SGRQ) will be evaluated using a linear mixed RE model. Within this model, the primary hypothesis about change in HRQOL from baseline to 6 months, will be evaluated by a hypothesis test of the interaction term between study group and the 6-month time variable.

For secondary outcomes, we will fit appropriate generalized linear mixed RE models based on the type of outcome variable. Continuous measures, such as for HERTH Hope Index or PROMIS support domain scores, will be assessed using linear mixed RE models. Binary outcomes, such as Morisky adherence to medication, will be assessed using logistic mixed RE models. Outcomes that are cumulative counts, such as number of hospitalizations and ED visits, will be assessed using Poisson or negative binomial mixed RE models, as appropriate. Differences in change in outcome from baseline to 3, 6, and 9-months between the study groups will be assessed by including interaction terms between the time variables and study group. We will assess significance by first testing the overall interaction between time and group. If the overall interaction is significant for an outcome measure, we will then estimate and test individual time differences accounting for multiple testing using a Bonferroni correction. Initially models will be adjusted only for baseline measure, site, and recruitment setting. We will also consider adjusting for patient characteristics such as age, gender, presence of caregiver, home oxygen use, and prior hospitalization.

Unadjusted survival analyses using Kaplan-Meier and log rank tests will be performed for *time to death or first COPD-related hospitalization or ED visit*. Statistical significance will be considered for $p < 0.05$.

Complier-Average Causal Effect (CACE) using Instrumental Variable Estimation

CACE: Primary Outcome

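### The one time-to-event comparison ignores the randomisation strata: its log-rank test is unadjusted and has no effect estimate, so it loses power if setting or site is prognostic

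*Combined protocol and SAP*

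**What the plan says.** Protocol section 4 (Study structure, note to the trial schematic) gives the allocation scheme: "Randomize within site and service setting". The SAP (Study Design) confirms the second factor, "Thus within each study site, patients were recruited from two clinical settings", namely inpatient and outpatient, and gives the ratio: "Then patients were randomized 1:1 to the HCP or the HCP PLUS Peer Support".

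The SAP (Statistical Analysis) sets the main analyses of change in the primary and secondary outcomes "under intention to treat (ITT) adjusted for baseline measure, site, and recruitment setting". Its paragraph on secondary outcomes makes those same factors the starting set of covariates, and protocol section 7c agrees.

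The same SAP section then says: "Unadjusted survival analyses using Kaplan-Meier and log rank tests will be performed for" "time to death or first COPD-related hospitalization or ED visit". The next sentence attaches a threshold: "Statistical significance will be considered for" p < 0.05. Neither document plans a stratified log-rank test, a Cox model, or a hazard ratio with an interval.

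**The concern.** An analysis should normally respect the factors used to restrict randomisation. Two separate things happen when a log-rank test ignores them.

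- **Power.** Pooling strata with different hazards dilutes the treatment contrast as the high-risk patients leave the risk set. This costs power whenever the strata are prognostic, however allocation was done.
- **Type I error.** If allocation is also forced into balance within strata, chance imbalance between strata is removed by design. The unstratified variance still allows for it, so the test rejects less often than its nominal 5%.

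Setting is a plausible predictor of this endpoint. Inpatients are enrolled during a hospital stay, and protocol section 3 quotes a re-hospitalisation figure of about 20% within 30 days of discharge. The two hospitals also serve different populations.

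At stake is a test that carries a significance threshold and bears on a stated hypothesis (SAP, Study Objectives, item b). The trial was sized on SGRQ, not on this composite, so a null result here could be misread as no benefit. A p-value without an estimate gives the reader no means of judging that.

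**Working it through.** **No plan figure to reproduce.** The documents state no event count, hazard ratio or power for this comparison. The 145 per arm in protocol section 7c is for SGRQ change, its SD is not given, and it does not bear on this point.

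**Inputs from the documents.** 290 patients (SAP, Study Design); 1:1 allocation; 2 sites × 2 settings = 4 strata; follow-up to 9 months, shorter for late enrollees; alpha 0.05, taken as two-sided because sidedness is not stated.

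**Assumed inputs.** Event rates, hazard ratios (HR) for setting and site, treatment HR, inpatient share, and blocks of 4 within strata.

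**Statistic.** Z = Σ(gⱼ − pⱼ) / √Σpⱼ(1 − pⱼ), summed over events. Here gⱼ is 1 if the patient with event j is in the peer-support arm, and pⱼ is that arm's share of those at risk. The unstratified test takes pⱼ over the whole trial. The stratified test takes it within the stratum and then adds the sums.

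**Check on the simulation.** Schoenfeld's formula is power = Φ(√(D/4)·|ln HR| − 1.96). With D = 104.5 events and HR 0.6, √26.125 × 0.511 − 1.96 = 0.65, so power is about 0.74. With no stratum effect the simulation gives 0.736.

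**Scenario A.** Four strata of equal expected size; exponential times; mean 9-month control risk fixed at 45% (about 105 events) or 25% (about 57 events); 30% of patients censored between 6 and 9 months; treatment HR 0.6; 10,000 null runs and 4,000 alternative runs. Each cell shows unstratified / stratified.

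| Control risk | Setting HR / site HR | Type I error | Power | Loss (points) |
|---|---|---|---|---|
| 45% | 1 / 1 | 0.050 / 0.050 | 0.736 / 0.733 | −0.3 |
| 45% | 1.5 / 1.2 | 0.042 / 0.046 | 0.734 / 0.736 | 0.2 |
| 45% | 2 / 1.3 | 0.042 / 0.050 | 0.714 / 0.734 | 2.0 |
| 45% | 3 / 1.5 | 0.034 / 0.047 | 0.692 / 0.743 | 5.1 |
| 45% | 5 / 2 | 0.024 / 0.051 | 0.634 / 0.750 | 11.6 |
| 25% | 1 / 1 | 0.047 / 0.046 | 0.460 / 0.461 | 0.1 |
| 25% | 1.5 / 1.2 | 0.051 / 0.053 | 0.467 / 0.471 | 0.4 |
| 25% | 2 / 1.3 | 0.044 / 0.048 | 0.472 / 0.474 | 0.2 |
| 25% | 3 / 1.5 | 0.042 / 0.050 | 0.449 / 0.475 | 2.6 |
| 25% | 5 / 2 | 0.036 / 0.052 | 0.434 / 0.491 | 5.7 |

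Monte Carlo error is about 0.002 for type I error and 0.008 for power. Both tests were run on the same simulated data sets.

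**Scenario B.** Outpatient control hazard 0.04 per month, site HR 1.2, half of patients inpatient, treatment HR 0.65. At the lower-risk site this means a 9-month control risk of 1 − e^(−0.36) = 30% for outpatients. For inpatients it is 1 − e^(−1.08) = 66% at setting HR 3 and 1 − e^(−1.44) = 76% at setting HR 4, so event rates here are high. Ranges are across repeated runs.

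- Setting HR 2: power 57–58% against 59%; unstratified type I error 4.4–4.7%.
- Setting HR 3: power 60–61% against 65–67%; type I error 3.3–3.4%.
- Setting HR 4: power 61–63% against 72–74%; type I error 2.7–2.8%.
- Setting HR 3 with 30% inpatients: 55% against 60%.
- Half the event rate: loss of about 1 point at HR 2 and 3 points at HR 3.

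**Simple randomisation instead of blocks.** Unstratified type I error returns to about 5% (0.048–0.052 in scenario A, 0.049–0.055 in B). The power loss remains: at setting HR 3, 68.1% against 74.0% (A, 45% risk), 45.6% against 47.0% (A, 25% risk), and 61% against 67% (B).

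**The case against.** The strongest reply is that this is a supporting analysis, openly labelled as unadjusted. The composite is not among the 13 numbered outcomes in the SAP. COPD-related visits and mortality are listed there separately, and visit counts go to Poisson or negative binomial mixed models adjusted for site and setting. Most of the composite's content therefore already has adjusted inference. All of that stands, and it keeps the point minor. It does not explain why a test with a p < 0.05 threshold should leave out the strata.

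Four stronger readings are tempting, and the documents do not support them.

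- **Every other analysis adjusts for site and setting.** The main outcome models do. The CACE section names no covariates, the participation model lists neither factor among its example predictors, and the subgroup section restates no adjustment.
- **The SAP breaks its own adjustment rule.** That rule is written for changes from baseline. A time to first event has no baseline value, so this is a gap in coverage rather than a contradiction.
- **The test is certainly conservative.** That requires prognostic strata and restricted allocation within them. The protocol mentions sealed envelopes but gives no block method.
- **The result would be invalid.** The error is toward caution, and no excess of false positives arises.

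It is also fair to say that the size of the loss rests wholly on assumed inputs. The 20% re-hospitalisation figure has no outpatient comparator, so it shows that a setting effect is plausible without measuring it.

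**Conclusion.** The point holds as a minor, low-cost improvement. Randomisation is within site and setting, the main outcome models respect this, and the only time-to-event comparison does not and reports no effect estimate.

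With allocation balanced within strata, and under the assumed event rates, the unstratified test loses about 0 to 2 points of power at a setting HR of 2, 3 to 7 points at 3, and 10 to 11 points at 4 when event rates are high. It loses nothing if the strata are not prognostic. Its type I error falls below nominal only if the strata are prognostic and allocation is restricted within them: about 3.3% to 4.2% at a setting HR of 3. The stratified test stays near 5% throughout (0.046 to 0.053 in scenario A) and shows no material power cost when the strata do not matter. The primary SGRQ analysis is unaffected.

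**What to change.** In the SAP's Statistical Analysis section, replace the unadjusted log-rank test with one stratified by site and recruitment setting, using the stratum in which the patient was randomised. Report a hazard ratio with 95% CI from a Cox model stratified the same way. Keep the Kaplan-Meier curves by arm as description, and note that they are marginal while the hazard ratio is conditional on stratum. State the method of allocation within strata and whether the test is two-sided.

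The cost is one or two sentences, with no new data. The SAP of June 2019 already reports enrolment as complete, so the change needs a dated, documented revision made before outcomes are compared by arm.

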Peer support group conversations will be orchestrated at 8 'Get Together' events spanning a 6 months period. All participants who miss an event or were not interested/able to attend an event (based on preference, life circumstances, or health status), will be offered the option of attending a similarly themed 'BREATHE group call' to catch up on missed event conversations and their 'matched' BREATHE Pal will also contact him/her via phone to check in on them, answer any questions they have, and encourage them to attend the next Get together event. At end of these phone calls, the peer mentor has the option of talking about their call with the social worker. If a patient or a family caregiver expressed the need for additional healthcare or social support services, or if the peer mentor felt that they need it, they would inform the social worker who will facilitate the patient or family-caregiver access to these services.

At the group events (in person or group call), the group participants led by the BREATHE Pals will discuss COPD and its challenges, and share their experiences in coping with and managing it. See summary table below on general topics for discussion. The topics pertain to advancing patient understanding of COPD and its treatment options, introducing effective coping skills, and reinforcing a variety of positive behaviors including adherence to treatment plans, smoking cessation, joining pulmonary rehabilitation programs, and assuming an active, healthy lifestyle. The Breathe pals will use the COPD Patient Education guide and a set of commonly asked questions and answers (Commonly Asked Questions and Answers) as their content guide/reference for the group conversations and follow up phone conversations. Each meeting will include: 1) Education about COPD management strategies based on the themes in table below; 2) discussion of patient experiences and challenges related to using these strategies; and, 3) encouragement to set goals and problem solve challenges. The sessions will follow a sequence of themes from 1-8 and then repeat. A study participant may thus join the sessions sequence at any time point and continue for 8 sessions thus getting to participate in all 8 themes. If at any point the number of participants attending the sessions exceeded 20 people, the group will be split into two and new participants may join either group according to their preferred group meeting time.

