All study participants will receive a Health Care Professional (HCP) support intervention in this study, which involves a 1 hour session with the respiratory care practitioner (RCP), and the ability to follow up with them with any questions. They would also receive the BREATHE binder with educational materials on COPD self-management and a resource guide.

Those randomized to the HCP PLUS Peer Support group of the study will also have the opportunity to participate in a Peer Support Program. This program will offer patients and their caregiver support services to be delivered via multiple channels including one-on-one and group conversations. In this program, the patient and caregiver participants will have the option to connect with other peers. Each patient and caregiver participant in this study group will be *matched* with a peer mentor (referred to as BREATHE Pal). The BREATHE pal will talk with the participant at regular intervals at peer group *Get together* events and/ or via phone. The group events will take place at the study sites, and will be co-led by two BREATHE Pals in the presence of a social worker. At these events, select topics about COPD self-management will be discussed, and the messages delivered by the respiratory care practitioner will be reinforced. Participants who are unable to attend these in-person events have the option to participate in BREATHE calls, where the same topics are discussed via a conference call.

Study Objectives

We hypothesize that the dual strategy of using *HCP PLUS Peer Support* to engage and support COPD patients and caregivers will have superior outcomes to the *HCP only* strategy at 3-, 6-, and 9-months post enrollment compared to baseline in the following areas:

- a) Improved health- related quality of life measured with the St. George's Respiratory Questionnaire.
- b) Improved survival and reduced numbers of COPD-related hospital and ED visits.

- c) Improved patient activation, self-efficacy, and self-care behaviors

Data Collection for Phase 2

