adherent participants all those patients who experienced at least four or more encounters with their peer mentor. We will also conduct sensitivity analyses in the same manner as for the primary outcome.

Intervention Implementation Analysis

In addition to assessing the primary and secondary outcomes for patients we intend to investigate which patient characteristics determine participation in the HCP PLUS Peer Support. That is, we will investigate which patient characteristics are related to attendance at BREATHE get togethers, participation in BREATHE calls, and phone interactions with BREATHE pals. As in the CACE analysis, we will define overall participation in the HCP PLUS Peer Support group as experiencing at least 4 or more encounters with a peer mentor either by attending a get-together, participating in a BREATHE call, or having a phone conversation. We will define participation in group support via attendance at 4 or more BREATHE get togethers or BREATHE calls. We will define participation in individualized 1:1 support by 4 or more encounters with a BREATHE pals over the phone. We will use multivariable logistic regression to predict overall participation, as well as participation in group or 1:1 support , from baseline characteristics such as age, gender, education level, distance from patient's home to meeting location, oxygen use, whether patient lives alone, whether patient reports they have a caregiver, self-reported health status, PAM level, and baseline assessments of hope, support, anxiety and depression from Herth Hope Index and PROMIS measures.

Heterogeneity of Treatment Effect (HTE) (PCORI Standard HT-1, HT-2, and HT-3)

HT-1, HT-3:

The goal of the HTE analyses in this study is to consider the difference in treatment effect between the two groups, taking into consideration differences in the groups that are not obviously accounted for in the balance created by the randomization scheme. Patient characteristics such as disease severity or caregivers' presence may show differences in the intervention's effect and thus are important avenues to explore for hypothesis generation. In these hypothesis generating HTE analyses, we will consider the following subgrouping variables for the primary outcome of change in SGRQ from baseline to 6 months: age (4 categories),

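### The participation analysis asks about get-togethers and BREATHE calls separately but models them only as one pooled group-support outcome, which may weaken or hide barriers to in-person attendance

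*Combined protocol and SAP*

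**What the plan says.** The SAP section Intervention Implementation Analysis states its aim by channel: "we will investigate which patient characteristics are related to attendance at BREATHE get togethers, participation in BREATHE calls, and phone interactions with BREATHE pals".

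It then defines three binary outcomes:

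- **Overall participation:** at least four encounters of any kind, as in the CACE analysis.
- **Group support:** "We will define participation in group support via attendance at 4 or more BREATHE get togethers or BREATHE calls".
- **1:1 support:** "We will define participation in individualized 1:1 support by 4 or more encounters with a BREATHE pals over the phone".

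The models follow those definitions: "We will use multivariable logistic regression to predict overall participation, as well as participation in group or 1:1 support". The baseline predictors include distance from "home to meeting location, oxygen use, whether patient lives alone", self-reported health status and others.

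Two other places describe what a BREATHE call is for. The SAP's Intervention Description says: "Participants who are unable to attend these in-person events have the option to participate in BREATHE calls". The protocol (section 4.a, Peer support program intervention) says that people who miss an event, or are not interested in or able to attend it, "will be offered the option of attending a similarly themed 'BREATHE group call' to catch up on missed event conversations". It adds that their matched BREATHE Pal will also phone them.

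**The concern.** The aim names three channels. Only phone contact gets its own outcome. Get-togethers and calls appear only inside the group outcome and the overall outcome, and no other section of the protocol or SAP defines either one alone.

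The two pooled channels are not independent. A call is what a patient is offered after missing an event, so the group outcome adds an activity to its own replacement. A characteristic that keeps patients away from the site lowers get-together attendance and increases the number of occasions on which a call is offered. Distance to the meeting location is the clearest case, because it bears on travel and has no obvious bearing on a phone call. Oxygen use may be another: the protocol's Background gives the need for portable oxygen as one reason why patients are reluctant to go out.

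At stake is whether the analysis can answer the question it sets. A weak or null association between distance and group support could mean that distance does not matter. It could equally mean that distance keeps people from events and calls make up the difference. The pooled model cannot tell these apart.

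**Working it through.** **Stated question against defined outcome** (SAP, Intervention Implementation Analysis)

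| Channel named in the aim | Own outcome? | Own model? |
|---|---|---|
| Get-togethers | No, pooled with calls | No |
| BREATHE calls | No, pooled with get-togethers | No |
| Phone contact with BREATHE Pal | Yes, four or more | Yes |

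This mismatch needs no assumption. The documents give no figure for this analysis, so there is none to reproduce. The rest illustrates how much pooling could matter.

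**Inputs from the documents.** 8 group sessions; a threshold of 4; 145 patients per arm (protocol section 7.c), with only the peer-support arm in this analysis.

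**Assumed inputs.** Half the patients live far from the site. In-person attendance per event is a = 50% near and 25% far. Call uptake after a missed event is c, varied below. The threshold is read as a combined count of get-togethers and calls.

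**Reach per theme.** A patient is reached by either route with probability q = a + (1 − a)c.

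**Simple check, same probability for everyone in a group.** P(at least 4 of 8 in person) is 0.637 near and 0.114 far, so the in-person odds ratio (far v near) is (0.114/0.886)/(0.637/0.363) = 0.07. The pooled outcome gives:

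- c = 25% in both: q = 0.625 v 0.4375, P = 0.863 v 0.494, odds ratio 0.16.
- c = 25% near, 40% far: q = 0.625 v 0.55, P = 0.863 v 0.740, odds ratio 0.45.
- c = 25% near, 50% far: q = 0.625 v 0.625, odds ratio 1.00.

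Exact cancellation requires equal q, that is c_far = (q_near − a_far)/(1 − a_far). With these attendance rates that is 0.33, 0.40, 0.50 or 0.67 when c_near is 0, 0.10, 0.25 or 0.50.

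**More realistic check, patients varying around the group means.** Beta-binomial simulation with n = 145, 8 themes, beta precision 3 and 1,500 replicates. Get-togethers are drawn from Bin(8, p) and calls from Bin(8 − attended, c), with p and c varying between patients. The table gives the median odds ratio (far v near) and the power of a two-sided 5% Wald test. The in-person outcome has an odds ratio of about 0.22 and power of about 99% in every row.

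| Call uptake near / far | q near / far | Pooled odds ratio | Power, pooled |
|---|---|---|---|
| 30% / 20% | 0.65 / 0.40 | about 0.21 | about 99% |
| 10% / 10% | 0.55 / 0.325 | 0.27 | 97% |
| 20% / 20% | 0.60 / 0.40 | 0.31 | 93% |
| 40% / 40% | 0.70 / 0.55 | 0.36 | about 75% |
| 30% / 40% | 0.65 / 0.55 | 0.53 | 41% |
| 30% / 50% | 0.65 / 0.625 | about 0.85 | about 7% |

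In the last row, four or more calls taken alone has an odds ratio of about 6 in the opposite direction. Separate models would show both associations; the pooled model shows almost neither.

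**The case against.** The strongest reply is that the pooled outcome is a proper quantity in its own right. The intervention consists of group support and 1:1 support, the SAP says that calls cover the same topics as the events, and the protocol treats in-person events and group calls alike as group events. If distant patients receive as much group support because calls fill the gap, then a null association with distance is a correct statement about reach. That stands, and it is why the pooled outcome should stay. It does not answer the question the SAP poses, which names the two channels separately.

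A second reply is that substitution is not assured. A patient who misses an event may take up the phone contact with the BREATHE Pal, or nothing. This also stands: calls are optional, and no uptake rates are given.

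A reader might therefore infer too much, namely that effects of distance and oxygen cancel out in the group outcome. The documents do not support that. Near-cancellation needs far patients to take up calls more often than near patients by a particular amount. With equal uptake a clear pooled association remains, and with lower uptake among far patients there is no attenuation. Only a generic near/far split was examined, so nothing numerical is shown for oxygen use or health status.

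**Conclusion.** The point holds as a mismatch between aim and outcome: two of the three channels the SAP says it will study have no outcome or model of their own. This does not depend on any assumed rate.

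The consequence is conditional. Associations of in-person barriers with attendance may be attenuated or masked. With assumed attendance of 50% near and 25% far, an in-person odds ratio of about 0.22 becomes a pooled odds ratio anywhere from about 0.21 to about 0.85 over the call-uptake rates examined. Attendance, call uptake, the near/far split and the between-patient variation are all assumptions.

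Two wider readings should be set aside. The SAP does not say that the analysis is meant to guide health systems in choosing a channel; it says only that it will look at which characteristics determine participation. Nor does the pooling reach the main results. The primary intention-to-treat test does not use the group outcome. The CACE analysis and the propensity-for-adherence subgroup rest on adherence, which follows the overall four-encounter definition. This is a low-priority improvement to a secondary analysis within one arm.

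**What to change.** In the SAP's Intervention Implementation Analysis:

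1. Add get-together attendance and BREATHE-call participation as two separate outcomes, modelled with the same baseline predictors.
2. Keep the pooled group outcome, described as a summary of group exposure by either route.
3. State whether the group threshold of four is a combined count of get-togethers and calls or four of one type.
4. Where calls can be linked to the events they replace, also report calls joined out of events missed, so that call uptake is not just the inverse of attendance. This is optional, because neither document describes a log with that link.

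The cost is some SAP wording and two more descriptive models, one of which may have few call users and so wide intervals. Items 1 to 3 should need no new data: applying the existing group and 1:1 definitions, and the CACE sensitivity definitions, already requires encounters to be recorded by type. The alternative is to narrow the stated aim to overall, group and 1:1 participation, which removes the mismatch but leaves in-person attendance unexamined.
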